4.5 Interim analyses

Interim analyses are planned at specific time point during phase 2 and phase 3 for identification of early superiority of reparixin (efficacy) or for early stop of the trial for futility.

O'Brien-Fleming spending functions will be used to control the type I and II errors for analyses of primary endpoints. P-values boundaries for efficacy and futility at interim and final analyses for phase 2 and phase 3 are reported in Table 4 and Table 5, respectively.

Table 4: O'Brien-Fleming spending functions boundaries for primary analysis in phase 2

Analysis	Sample Size	Boundaries for primary endpoint	
		Efficacy	Futility
Interim #1	~27 (23 events)	p-value < 0.00258	p-value ≥ 0.23349
Final	48 (46 events)	p-value < 0.02400	p-value ≥ 0.02400

Table 5: O'Brien-Fleming spending functions boundaries for primary analysis in phase 3

Analysis	Sample Size	Boundaries for primary endpoint	
		Efficacy	Futility
Interim #1	~60 (60 events)	p-value < 0.00296	p-value ≥ 0.26674
Interim #2	~81 (81 events)	p-value < 0.00892	p-value ≥ 0.09841
Final	111 (109 events)	p-value < 0.02151	p-value ≥ 0.02151

The interim analyses will be conducted by DMC who will communicate to the Sponsor the result of the interim analysis and the consequent decision on the continuation of the study.

The following scenarios may emerge from the interim analysis:

- the communication from the DMC to the Sponsor will be "Not enough evidence for demonstrate superiority of reparixin". Since results are not considered enough to draw conclusions on primary

endpoints, the study enrolment will continue up to the next analysis step, and treatments and follow-ups will proceed without modifications.

- the communication from the DMC to the Sponsor will be “Superiority of reparixin is shown”. In this case, the following action will be taken according to the study phase:
 - Phase 2:
 - enrollment of subjects in phase 2 is stopped
 - already enrolled subjects continue their residual treatment and follow-up as planned
 - adaptation of phase 3, if needed;
 - enrollment of subjects in phase 3 may start;
 - Phase 3:
 - enrollment of subjects is stopped
 - already enrolled subjects continue their residual treatment and follow-up as planned
 - when last enrolled subject completes the follow-up and database is close, final analysis is performed and clinical study report will be released.
- the communication from the DMC to the Sponsor will be “Superiority of reparixin is excluded”. In this case, independently from the study phase, the enrollment (if still ongoing) will be stopped, and all subjects will discontinue the treatment and will be follow-up till the next scheduled visit where they will be notified of the termination of the study.

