## - Phase 2/3 Exclusion Criteria:

- 1. Cannot obtain informed consent.
- 2. Severe hepatic dysfunction (Child Pugh score  $\geq$  C, or AST> 5 times the upper limit); Severe renal dysfunction (estimated glomerular filtration rate  $\leq$  30mL / min / 1.73 m2) or receive continuous renal replacement therapy, hemodialysis, or peritoneal dialysis.
- 3. Patients with hypersensitivity to ibuprofen or to more than one non steroidal anti-inflammatory drug or to more than one medication belonging to the class of sulfonamides (e.g.

sulfamethazine, sulfamethoxazole, sulfasalazine, nimesulide or celecoxib; hypersensitivity to sulphanilamide antibiotics alone, e.g. sulfamethoxazole, does not qualify for exclusion)

- 4. Severe, active bleeding such as hemoptysis, gastrointestinal bleeding, central nervous system bleeding, and nosebleeds within 1 month before enrollment.
- 5. Pregnant and lactating women and those planning to get pregnant.
- 6. Participated in other interventional clinical trials with investigational medicinal products, not considered suitable for this study by the researchers.
- 7. At the time of enrollment, patients not in a clinical condition compatible with the oral administration of the study drug.

**Number of patients enrolled:** It is planned that 48 patients will be enrolled in Phase 2 and a total of 111 patients will be enrolled up to completion of the Phase 3. However, the sample size for the Phase 3 segment of this study may be re-estimated based on the Phase 2 results. In the current sample size scenario, 32 patients will receive Reparixin in Phase 2.

**Study duration:** treatment duration will be up to a maximum of 21 days. Overall Phase 2 study duration will be maximum 1 month (including 21 days of treatment and up to 7±3 days of follow-up).

**End of study (EOS) definition:** EOS is defined as the last day the last patient completes the last study assessment in the hospital, or retracts the consent to participate in the study, or withdraws from the study, or is deceased or otherwise lost to follow-up.

**Interventions:** Patients who satisfy the predefined inclusion and exclusion criteria for this trial will be randomized 2:1 to one of the following treatment groups:

- **GROUP 1:** Reparixin oral tablets 1200 mg TID for 7 days. **In case of improvement**, treatment can be prolonged at discretion of the investigator up to a maximum of 21 days of treatment in total or live discharge from the hospital, whichever comes first.

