## 7.3.3 RECORDING

AEs will be collected and recorded for any untoward event that occurs in a patient from the time he or she signs the Informed Consent for the trial until the end of the follow up period. Thus, any untoward medical occurrences or unfavorable and unintended signs, symptoms, or diseases that occur in the pretreatment, in treatment, or post treatment period are to be considered AEs and/or SAEs, and consequently recorded and reported as such. Should a non-serious AE become serious, the Investigator will then follow the same reporting procedures as for SAEs.

Each AE will be described by:

- Its duration (start and stop dates).
- Its seriousness.
- Its relationship to the study drug (suspected/unsuspected).
- Action(s) taken.
- Outcome.

Medical conditions/diseases and related signs/symptoms present before starting study treatment shall be documented in the medical history section of the CRF; these conditions are considered AEs only if they increase either in frequency or severity once informed consent has been signed.

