#### 7.3.5 FOLLOW-UP OF PATIENTS WITH ADVERSE EVENTS

The Investigator is responsible for adequate and safe medical care of subjects during the trial and for ensuring that appropriate medical care and relevant follow-up procedures are maintained after the trial. All AEs should be followed-up to determine outcome of the reaction. The Investigator should follow up the event until resolution or stabilization of the condition. It is the Investigator's responsibility to ensure that the subjects experiencing AEs receive definite treatment for any AE, if required.

If subject was hospitalized due to a SAE, a copy of the discharge summary is to be forwarded to the Sponsor as soon as it becomes available.

In addition, a letter from the Investigator that summarizes the events related to the case as well as results of any relevant laboratory tests also may be requested. Further, depending upon the nature of the SAE, Dompé may request copies of applicable segments of the patient's medical records. In case of death, a copy of the autopsy report, if performed, should also be provided.

The Investigator shall inform the Sponsor with an appropriate written communication, whenever he becomes aware of new available information regarding the SAE, once the condition is resolved or

stabilized and when no more information about the event is expected. Follow-up SAE information should be processed as initial SAE notification (see Par. 7.3.6).

For pharmacovigilance purposes, all SAEs should be followed-up in order to clarify as completely as possible their nature and/or causality and until all queries have been resolved. All SAEs will be followed up until the events resolve or the events or sequelae stabilize, or it is unlikely that any additional information can be obtained after demonstration of due diligence with follow-up efforts (i.e. subject or Investigator is unable to provide additional information, or the subject is lost to follow up), unless subject has withdrawn his/her consent.

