#### 8.2 Discontinuation and Withdrawal

A patient has the right to withdraw from this clinical trial at any time and for any reason, without any repercussion.

The investigators also have the right to withdraw a patient from the study at any time if in their opinion it is no longer in the best interest of the patient to remain in the study.

As no withdrawals have been anticipated in the sample size calculations, patients who are withdrawn before completing the minimum of 24hrs treatment with the oral tablets in the active group can be replaced to reach the predefined samples size of the Phase 2 segment of the study. Participants who whitdraw from the study cannot be re-randomized.

Considerations on withdrawals for the Phase 3 segment of the study will be reassessed.

All discontinuations must be recorded by the investigators and reported to the Sponsor and, if possibile, an early discontinuation visit should be conducted and data recorded.

Temporary discontinuation or drug discontinuation is not allowed since treatment with the medication is planned for continuous use throughout the treatment phase.

Patients will be followed-up according to the study procedures set forth in this clinical trial protocol and until the scheduled last day of follow-up. The only exception will be the collection and reporting of AEs that have occurred during the clinical trial and have not resolved by the time of the end of follow-up: in this case AEs will be followed until resolution or stabilization.

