3.2 Sample size justification

The sample size of the full phase 2/3 study is calculated based on data from clinical experience and on Sponsor expectations as reported in Table 2:

Table 2: Assumptions for primary endpoints

Primary endpoint*	Standard of care (control)	Reparixin
Time to primary endpoint of phase 2	2 days	5 days
Time to primary endpoint of phase 3	2-4 days	4-8 days

* see section 3.5.1.

Based on the following assumptions:

- an enrollment phase of 2 months,

- a total follow-up of 21 days,
- a randomization ratio (reparixin:control) of 2:1
- an exponential distribution for survival probability $S(t) = e^{-\lambda t}$,
- a comparison between treatment by means of a log-rank test,
- an interim analysis framework as described in section 4.5, and
- a correction of the type I and II errors by means of O'Brien-Fleming spending functions

a total of 109 events (corresponding to approximately 111 subjects) will allow to provide >80% power to show superiority of reparixin vs standard of care in terms of primary endpoint of phase 3, controlling the type I error under 0.025.

Based on the same assumptions reported above, phase 2 portion of the study will be performed when a total of 46 events (corresponding to approximately 48 subjects) has happened. This allow to achieve approximately 80% power to show superiority of reparixin vs standard of care in terms of (not severe) primary endpoint of phase 2, controlling the type I error under 0.025.

The remaining portion of the 111 patients will be enrolled in the phase 3 study segment. Anyhow, due to the novel nature of the COVID-19 pandemic and being the primary efficacy endpoint planned in phase 3 not well established, it may require confirmation based on phase 2 data. For this reason, at the end of the phase 2 portion, power calculations may be reassessed, and sample size may be re-estimated for phase 3.

The adaptive design allows for the assessment of efficacy endpoint in phase 2 which are then seamlessly confirmed in the phase 3. Since primary endpoint of phase 3 will be tested only if superiority of reparixin is shown in phase 2 (at interim or final stage), the overall type I error of the study will be controlled at 0.025 via the hierarchical testing procedure.

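### After a futility stop, SAP 4.5 ends follow-up at the next scheduled visit, contrary to the protocol's follow-up and AE-recording rules

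*SAP*

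**What the plan says.** SAP 4.5 lists three messages that the DMC can send after an interim analysis. If superiority is ruled out, in either phase, enrolment stops and "all subjects will discontinue the treatment and will be follow-up till the next scheduled visit where they will be notified of the termination". If superiority is shown, the same section says that "already enrolled subjects continue their residual treatment and follow-up as planned".

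The protocol's rules are these:

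- Section 8.2: "Patients will be followed-up according to the study procedures set forth in this clinical trial protocol and until the scheduled last day of follow-up". The sentence that follows names one exception, for adverse events unresolved at the end of follow-up, and it extends observation.
- Section 7.3.3: adverse events are recorded "from the time he or she signs the Informed Consent for the trial until the end of the follow up period", and the post-treatment period is expressly included.
- Section 1, study duration (phase 2): the maximum is one month, "including 21 days of treatment and up to 7±3 days of follow-up".
- Section 7.3.5: "All SAEs will be followed up until the events resolve or the events or sequelae stabilize".

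Both schedules of evaluations list Screening, Baseline, Day 1, Day 2, Week 1, End of treatment and End of follow-up. The last visit carries AE/SAE recording, the clinical severity score, laboratory tests and the second pregnancy test. SAP 4.9 states that no change to the planned analysis was made.

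**The concern.** The SAP sets a shorter follow-up for one interim outcome than the protocol allows, and does not say so. A site or data manager who applies SAP 4.5 as written would close out subjects whom protocol 8.2 and 7.3.3 require to be followed further.

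What is at stake is active ascertainment after the last dose: new-onset adverse events, vital status at a planned visit and the End of follow-up assessments. The subjects exposed are those still on treatment when the message arrives, so they are the most recently dosed. The shortening applies only after an unfavourable interim result. If reparixin has no effect, that is the result the design is most likely to produce.

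**Working it through.** **1. The passages side by side**

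| Question | SAP 4.5, superiority ruled out | Protocol |
|---|---|---|
| Follow-up ends | Next scheduled visit | Scheduled last day (8.2) |
| Exceptions | None stated | One, which lengthens follow-up (8.2) |
| AE recording ends | By implication, at that visit | End of the follow-up period (7.3.3) |
| Planned time after treatment | Not guaranteed | Up to 7±3 days, i.e. 4 to 10 (section 1) |

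Protocol 5.1 allows enrolment or the study to be interrupted for futility. It gives no shorter follow-up for that case.

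**2. The plan's own bounds.** Inputs from SAP 3.2 and 4.5: interim at 23 of 46 events, one-sided level 0.025, 2:1 allocation, 2 versus 5 days (hazard ratio 2/5 = 0.4 under the exponential model). A classical two-look O'Brien-Fleming design at information 0.5 and 1 gives 0.00258 and 0.02400, the values in SAP Table 4. As a check, p = 0.02400 is z = 1.977, and 1.977/√0.5 = 2.796, which is one-sided p = 0.00258. Simulating the design with both sets of bounds (1,000,000 runs) gives 80.1% power, against about 80% stated. The table is therefore on the one-sided p-value scale.

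**3. How often the futility bound is crossed.**

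- Hazard ratio 1: the one-sided p-value is approximately uniform, so P(p ≥ 0.23349) = 1 − 0.23349 = 76.7% at the phase 2 interim. The efficacy bound is crossed 0.26% of the time.
- Hazard ratio 0.4: information is 23 × 2/3 × 1/3 = 5.11. The mean of Z is −ln(0.4) × √5.11 = 0.916 × 2.261 = 2.07, and the bound is z = 0.727. P = Φ(0.727 − 2.07) = 8.9%.
- Phase 3, hazard ratio 1: 1 − 0.26674 = 73.3% at the first interim. Simulation gives about 90.8% by the second.

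**4. Observation left after stopping.** Assumptions: nominal visits on Days 1, 2 and 7, stopping times uniform over the course, and the stop does not itself trigger the End of treatment visit.

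- 7-day course: the gap to the next visit averages 0.5 days for a stop in the first day, 0.5 in the second, and 2.5 from Day 2 to Day 7. Mean = (1 × 0.5 + 1 × 0.5 + 5 × 2.5)/7 = 1.9 days; range 0 to 5.
- 21-day course, End of treatment on Day 21: mean = (13.5 + 14 × 7)/21 = 5.3 days; range 0 to 14. The gap is under 7 days for 14/21 = 67% of stopping times.

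**5. Dependence on an undefined term.** End of treatment has no fixed calendar day, and SAP 4.5 stops treatment in everyone. Three readings are open:

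- calendar visits continue, with the result in step 4;
- End of treatment is brought forward and counts as the next scheduled visit, leaving about zero days;
- the stop counts as End of treatment already done, so the next visit is End of follow-up and nothing is lost.

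**6. Who is exposed.** About 27 patients are enrolled at the phase 2 interim (SAP Table 4). At 2:1 that is 27 × 2/3 = 18 on reparixin and 9 on control. Only those not yet past End of treatment can lose anything.

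**The case against.** The strongest reply is that the protocol governs follow-up and AE collection, while the SAP calls itself general guidelines. Protocol 9.4.1 also lists early closure among the adaptations to be detailed in the SAP. That explains why the SAP addresses the matter. It does not license a stated rule that shortens what protocol 8.2 fixes with a single exception.

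Several limits do stand:

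- Known AEs are followed to resolution or stabilisation (7.3.5), continuing SAEs are still reported after participation (7.3.6), and death is always an SAE (7.3.1). A reader might infer that late deaths and SAEs are lost. The documents do not support that. An SAE that the investigator learns of after participation must still be reported. However, 7.3.6 adds that active monitoring is not usually needed once the trial has ended, so detection of new events becomes passive.
- The rule covers all subjects. A reader might see a bias between arms, but reparixin and control are shortened alike. Failing to show superiority is also not evidence of harm.
- Protocol 9.4.5 calls futility non-binding, so 76.7% is the chance of crossing the bound, not of stopping.
- A reader might scale exposure from the full 111 patients. At the phase 2 interim the ceiling is about 27, and phase 3 starts only after an amendment (SAP 4.7).
- A reader might infer that patients are kept uninformed until the visit. The text speaks of notice of study termination. In an open-label inpatient trial a patient would know that treatment had stopped. This is a matter of conduct and adds nothing to the conflict.
- Protocol 10.1.3 reports an oral half-life of about 2 hours without accumulation, so residual exposure is short. That does not settle disease-related outcomes.

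**Conclusion.** The concern holds as a direct, undeclared conflict between SAP 4.5 and protocol 8.2 and 7.3.3 on how long subjects are followed after a futility stop. The possible loss is active collection of new-onset events, mainly non-serious ones, and of the End of follow-up assessments, in subjects still on treatment. Its size runs from nothing to the whole post-treatment window, depending on how the next scheduled visit is read. The 0 to 5 day figure rests on the step 4 assumptions for a 7-day course. Subjects already past End of treatment are unaffected on any reading.

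The outcome that triggers the rule is the expected one if the drug has no effect, provided the DMC follows the bound. Alpha, power and sample size are not affected. The SAP wording should be corrected.

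**What to change.** In SAP 4.5, replace follow-up to the next scheduled visit with follow-up of every randomized subject through the planned End of follow-up visit, including AE/SAE recording, vital status and the pregnancy test. This is consistent with protocol 8.2 and 7.3.3. State how the End of treatment visit is handled when treatment is stopped by this decision, so that the later visit is dated from a defined point. If a shorter follow-up is really intended, the protocol has to say so and SAP 4.9 has to list it as a change.

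The passages on ongoing treatment after each DMC message should be reconciled with the protocol. No position is taken here on that decision.

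The cost is a wording change and roughly one more week of data collection per affected subject, which the protocol already plans.

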4.6 DMC Safety Integrity Review

In addition to the above interim analyses, analysis of safety data will be performed for supporting Safety Integrity Review meetings during the trial.

Safety Integrity Review meetings will be performed on ongoing basis (frequency will be defined by DMC members also considering feedbacks from REPAVID-19 Investigators) and at the end of the phase 2 in order to ensure that, in addition to superiority in efficacy, reparixin has an adequate safety profile.

The following information will be analyzed for safety reason at each Safety Integrity Review:

- Major protocol changes,
- Information on subject screening,
- Study accrual by month and by institution,
- Eligibility violations,
- Demographics,
- Length of follow-up data available (pooled by treatment regimen),
- Analyses of adverse events,
- Analyses of vital signs, including basic summaries and longitudinal analyses,
- Analyses of lab values, including basic summaries and longitudinal analyses,
- Discontinuation of medications,
- Information on crossover subjects.

4.7 Study adaptation

REPAVID-19 trial's design will allow for adaptations based on results from efficacy and safety data through the study. The spectrum of possible adaptations for the phase 3 study segment with the corresponding trigger rules is reported in Table 6.

In case of decision of continuation of the study, results of the phase 2 portion of study will be submitted to the competent authority with the final version of the Phase 3 segment of the study (as an amendment to study protocol) prior to proceed. In that case, the SAP will be updated accordingly.

Table 6: Adaptations and triggers

Action	Trigger
Modification of the experimental treatment route of administration.	Safety reasons based on DMC recommendation or Sponsor evaluation.
Confirmation or modification of the primary, secondary and exploratory endpoints (at beginning of phase 3).	DMC indication based on review of phase 2 results.
Refining the sample size.	In case of relevant discrepancies between sample size assumptions (section 3.2) and phase 2 results.
Population enrichment.	Based on safety and efficacy results (including subgroup analyses), it may be identified a subset of subjects most likely to benefit from treatment.
Change the allocation ratio of subjects to trial arms.	Safety and ethical reasons based on DMC recommendation or Sponsor evaluation.

4.8 Handling of missing and incomplete data

The number of subjects with missing data will be presented under the "Missing" category, if present. Missing values will not be included in the denominator count when computing percentages. Similarly, only the non-missing values will be evaluated for computing summary statistics for continuous endpoint. Any exception will be clarified as a note.

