### - Phase 2/3 Study Endpoints:

- **Primary Endpoint for Phase 2:** Composite endpoint of clinical events (the patient requires at least one of the following: supplemental oxygen requirement, mechanical ventilation use, admission to ICU, and use of a rescue medication for any reason)
- **Primary Endpoint for Phase 3:** Composite endpoint of death and clinical severe events (the patient dies or requires mechanical ventilation use and/or admission to ICU)
- Secondary Endpoints:
  - Changes in clinical severity score (as recommended by WHO for COVID studies), defined as the time to clinical improvement of two points from the time of randomization on a seven-category ordinal scale or live discharge from the hospital, whichever comes first. The seven-category ordinal scale consists of the following: 1) not hospitalized, with resumption of normal activities; 2) not hospitalized, but unable to resume normal activities; 3) hospitalized, not requiring supplemental oxygen; 4) hospitalized, requiring supplemental oxygen; 5) hospitalized, requiring high-flow oxygen therapy, noninvasive mechanical ventilation, or both; 6) hospitalized, requiring ECMO, invasive mechanical ventilation, or both; and 7) death.
  - Dyspnea severity (Liker scale and VAS scale)
  - Changes in body temperature
  - Changes hematology test values
  - o Duration and quantity of supplemental oxygen treatment
  - Incidence and duration of mechanical ventilation use
  - o Incidence of intensive care unit (ICU) admission need
  - Lung damage extension changes from baseline (assessed by Chest CT or Rx)
  - Change from baseline in lung exudation degree (assessed by Chest CT or Rx)
  - o PaO2
  - o SpO2
  - Partial arterioral oxygen pressure (PaO2) to fraction of inspiration O2 (FiO2) ratio
  - o CRP
  - o Hs-CRP

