#### 8 END OF STUDY, DISCONTINUATION AND WITHDRAWAL

#### 8.1 End of study (EOS):

The EOS is defined as the last day the last patient completes the last study assessment in the hospital, or retracts the consent to participate in the study, or withdraws from the study, or is deceased or otherwise lost to follow-up.

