7.2.2 Comparison between treatments

Along with the above summary statistics, comparisons between treatments will be performed as detailed in the next sub-sections. Parametric test (i.e. two-sample t-test for continuous variables, Chi-square test for categorical) will be adopted as first choice. In case the required assumptions are not met, the corresponding non-parametric counterpart will be used (i.e. the two-sample Mann–Whitney U test for continuous variables, and the Fisher’s Exact test for the categorical). Normality of continuous data is assessed by Kolmogorov-Smirnov test.

Comparison will be performed at each available time point, where applicable. Any exception will be declared.

7.2.2.1 *Composite endpoint of phase 2 using Oxygen Delivery System Classification*

The composite endpoints will be summarized along with their single component by a binomial response rate at each time point (only the first event will be considered). The Clopper-Pearson method will be used to estimate the two-sided 95% CIs.

Time to composite endpoint(s) will be performed using the KM methodology and the one-sided log-rank test will be used to test for differences between treatment groups.

7.2.2.2 *Changes in clinical severity score*

Number and proportion along with the 95% confidence interval (Clopper-Pearson’s formula) of subjects with a clinical severity score improvement of at least two points compared to randomization or live discharge from the hospital will be calculated and compared.

7.2.2.3 *Dyspnea severity (Liker scale and VAS scale)*

The comparison of the Liker scale between the two study treatment arms will be performed by means of Wilcoxon signed-rank test, given its ordinal nature.

Number and proportion along with the 95% confidence interval (Clopper-Pearson’s formula) of subjects with

any improvement (improved vs not-improved) will be calculated and compared.

VAS scale comparison between treatments will be performed according to its continuous nature.

7.2.2.4 *Changes in body temperature*

Comparison between treatments in change from baseline of the body temperature will be performed according to the continuous nature of the variable.

7.2.2.5 *Incidence of supplemental oxygen treatment*

Number and proportion along with the 95% confidence interval (Clopper-Pearson's formula) of subjects who worsened according to PaO₂/FiO₂ and to Oxygen Delivery System Classification based on oxygen support will be calculated and compared.

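### For the Liker any-improvement proportion, SAP 4.8 drops patients who have died from later-visit denominators; for the severity-score responder, no derivation rule prevents the same loss.

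*SAP*

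**What the plan says.** **Denominator rule.** SAP 4.8 says "Missing values will not be included in the denominator count when computing percentages". Protocol 9.4.1 contains the same sentence. SAP 4.8 also displays the count of missing patients as a separate category and adds "Any exception will be clarified as a note". It specifies no exception for the endpoints discussed here.

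**Liker proportion.** SAP 7.2.2.3 calculates and compares the proportion of patients with any improvement, with a Clopper-Pearson interval. Protocol 7.2 describes the scale as the patient's own grading of breathing from -3 to 3. SAP Table 7 defines which answers count as improved and says nothing about patients who have died.

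**Severity-score responder.** SAP 7.2.2.2 counts "subjects with a clinical severity score improvement of at least two points compared to randomization or live discharge from the hospital". On the seven-category scale in Protocol section 3, categories 1 and 2 are the non-hospitalised states, and the scale ends "6) hospitalized, requiring ECMO, invasive mechanical ventilation, or both; and 7) death".

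**Timing and population.** SAP 7.2.2 says "Comparison will be performed at each available time point, where applicable". SAP 4.2.4 analyses the FAS by allocation, whatever intercurrent events occur.

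**The concern.** Neither 7.2.2.2 nor 7.2.2.3 states a denominator, so 4.8 applies by default. In hospitalised patients with severe COVID-19 pneumonia, the main reason that a Liker answer can never be given at a later visit is death. A rule written for ordinary missing data then turns the comparison of randomised groups into one of survivors. An arm can gain in percentage terms because more of its patients died. This also sits badly with the FAS commitment in SAP 4.2.4.

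The SAP recognises the problem elsewhere: its section 7.1.3.1 adds death to a modified phase 2 composite so that censoring by fatal events can be examined. The responder proportions have no such safeguard. What is at stake is the size and direction of secondary estimates, with their intervals and p-values.

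**Working it through.** The plan gives no rate, power or expected value for these proportions, so there is no figure to reproduce. The check has two parts.

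**1. Does any text override SAP 4.8 for death?**
- SAP 7.2.2.2 and 7.2.2.3 state no denominator.
- SAP Table 7 has no row for the severity-score responder. Its Liker row lists only the improved answers.
- The DEATH REPORT form is named in only two derivations, the modified phase 2 composite and the phase 3 composite.
- SAP 9.2 deals with partial dates for adverse events and medications only.
- Protocol 9.4.2.3 describes efforts to limit missing data and gives no analysis rule.

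So nothing overrides it. For Liker, removal after death follows directly from the text. For the severity score, a patient recorded as 7 has a value and is a non-responder, and a patient discharged alive is a responder. Removal there needs the further step that no score is entered or derived at the later visit.

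**2. How large is the effect?**

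Let n be the patients in an arm, x those improved, d the fraction dead by the visit, and p = x/n. Assume that every survivor has a value and that no patient who died counts as improved. Then:
- all patients: x/n = p
- SAP 4.8: x/(n - nd) = p/(1-d)

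At p = 50%, 0.50/0.90 = 55.6% and 0.50/0.75 = 66.7%. The rise in percentage points, on assumed rates, is:

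| p | d = 5% | d = 10% | d = 15% | d = 20% | d = 25% |
|---|---|---|---|---|---|
| 40% | 2.1 | 4.4 | 7.1 | 10.0 | 13.3 |
| 50% | 2.6 | 5.6 | 8.8 | 12.5 | 16.7 |
| 60% | 3.2 | 6.7 | 10.6 | 15.0 | 20.0 |

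Phase 2 arm sizes come from the Protocol summary: 32 of 48 on reparixin, so 48 - 32 = 16 on control. Responder and death counts below are assumed.

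| Responders (reparixin; control) | Deaths | All patients | SAP 4.8 | Difference, all patients | Difference, SAP 4.8 |
|---|---|---|---|---|---|
| 16/32; 8/16 | 8; 1 | 50.0% vs 50.0% | 16/24 = 66.7% vs 8/15 = 53.3% | 0.0 | +13.3 |
| 16/32; 8/16 | 4; 2 | 50.0% vs 50.0% | 16/28 = 57.1% vs 8/14 = 57.1% | 0.0 | 0.0 |
| 16/32; 8/16 | 0; 4 | 50.0% vs 50.0% | 16/32 = 50.0% vs 8/12 = 66.7% | 0.0 | -16.7 |
| 16/32; 9/16 | 8; 1 | 50.0% vs 56.3% | 16/24 = 66.7% vs 9/15 = 60.0% | -6.3 | +6.7 |

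In the last row the direction reverses in favour of the arm with 25% deaths. Fisher's exact p-values under SAP 4.8 are 0.51, 1.00, 0.50 and 0.74 in row order.

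With equal death fractions but unequal response, the difference becomes (p1 - p2)/(1-d): it is stretched but keeps its sign. A false difference between equal arms, or a reversal, needs unequal deaths.

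**The case against.** A reader might infer that the severity-score proportion also leaves out the dead and the discharged as a matter of course. The documents do not support that. Death is a scale category, so a patient who died has a defined, unfavourable value, and live discharge is written into the response definition. A scenario in which discharged patients vanish from this proportion contradicts the endpoint text.

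Nor does Protocol 8.1 show that no record exists after a patient leaves hospital. Its phrase "last patient completes the last study assessment in the hospital" defines the end of the whole trial, not a patient's last visit. Protocol 8.2 follows patients to the scheduled last day of follow-up, and the schedule of evaluations lists both the severity score and the Liker scale at that visit. Whether a score is entered after death or discharge depends on the case report form, which is not available here.

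It would also be too broad to say that 4.8 distorts every percentage. Missing counts are shown, noted exceptions are allowed, and SAP 5.1 sets its own denominators for disposition.

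Excess deaths would not be hidden. SAP 8.1 tabulates and lists deaths by arm, SAP 7.1.3.1 includes the death-augmented composite, and SAP 7.1.2 analyses the phase 3 composite, which contains death, in phase 2 as well. The decision to proceed rests on the primary analysis alone.

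Finally, describing dyspnea only among patients able to answer, with deaths reported separately, is a legitimate choice of question.

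All of this limits the point without removing it. A displayed missing count does not correct the percentage, interval or p-value beside it. A survivors-only question can be chosen, but the SAP does not say that it has chosen one, and its FAS definition points the other way.

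**Conclusion.** The point holds for the Liker any-improvement proportion: followed as written, the plan removes patients who have died from later-visit denominators and raises p to p/(1-d). For the severity-score responder it is a narrower gap. The definition handles death and live discharge correctly, but no derivation ensures that those values are present at later visits.

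The size rests on assumed rates, since the documents give none. At p = 50% the rise is 5.6 points with 10% deaths and 16.7 points with 25%. At 32 versus 16 patients none of the illustrated differences reaches significance, so the risk is to estimates and their direction more than to a formal claim. Only secondary endpoints are affected; the primary log-rank analysis and the decision to proceed to phase 3 are not. This is a worthwhile, inexpensive correction, not a flaw in the main conclusion.

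**What to change.** In SAP 4.8 and Table 7:
- For the 7.2.2.2 proportion, make all FAS patients the denominator at every time point.
- Derive severity category 7 from the DEATH REPORT form at all time points after death, and carry live discharge forward as response.
- For the 7.2.2.3 Liker proportion, count death before the visit as not improved, and show the observed-only proportion as a sensitivity analysis.

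The cost is a few sentences in the SAP and a few lines of programming before database lock. Death already has its own form, and live discharge is already part of the 7.2.2.2 definition. The downside is that absence of a Liker answer because of death is scored rather than left missing. The main Liker proportion then no longer describes dyspnea among survivors alone, which is why the observed-only version should be kept beside it.
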